4.4.7. Change from baseline and Percent change from baseline

Change from baseline is defined as: Change from baseline = Value at specific time point – Baseline value

Percent change from baseline is defined as:

$$\text{Percent change from baseline}(\%) = \frac{\text{Value at specific timepoint} - \text{Baseline value}}{\text{Baseline value}} \times 100\%$$

4.5. Intercurrent Event Types

Table 4.5.1 specifies the types of Intercurrent events (IcEvs), and associated labels, used to define the estimands.

Table 4.5.1 Intercurrent Event Types

Label	Intercurrent Event Type
IcEv1 (discontinuation or interruption of study treatment due to Covid-19)	Treatment discontinuation or interruption due to Covid-19
IcEv2 (discontinuation or interruption of study treatment not due to Covid-19)	Treatment discontinuation or interruption not due to Covid-19
IcEv3 (Rescue Meds)	Use of rescue medications
IcEv4 (Prohibited Meds)	Use of prohibited medications

5. Patient Disposition

5.1. Disposition

The patient disposition will be summarized for the ITT analysis set by treatment group and overall using number and percentage. This section describes patient disposition for both patient study status and the patient analysis sets.

For patient study status, the number and percentage of patients in the following categories will be presented:

- Screened patients
- Screen failure patients
- Patients treated without being randomized
- Randomized patients
- Randomized but not treated patients

- Randomized and treated patients
- Patients who have completed treatment during the double-blind treatment period
- Patients who did not complete treatment during the double-blind treatment period and the main reason for treatment discontinuation. Relationship with COVID-19 will be reported for “Adverse Event” and “Other” reasons will be summarized too.
- Patients who discontinued the study during the double-blind treatment period and the main reason for study discontinuation. Relationship with COVID-19 will be reported for “Adverse Event” and “Other” reasons will be summarized too.
- Patients who entered into open-label extension treatment period (OLE)
- Patients who did not complete treatment during the OLE treatment period and the main reason for treatment discontinuation. Relationship with COVID-19 will be reported for “Adverse Event” and “Other” reasons will be summarized too.
- Patients who completed study
- Patients who discontinued the study during the OLE treatment period and the main reason for study discontinuation. Relationship with COVID-19 will be reported for “Adverse Event” and “Other” reasons will be summarized too.
- Patients who had rescue medications (see [Section 15.11](#))
 - Patients who have completed the double-blind treatment period and had rescue medications
 - Patients who did not complete the double-blind treatment period and had rescue medications
- Final Study Status

For screened, screen failure, and patients treated without being randomized, percentages will be calculated using the number of screened patients as the denominator for overall only. All other categories of patients will be presented by treatment group and for overall and the percentages will be calculated using the number of randomized patients within each treatment group and overall, as denominator. Reasons for treatment discontinuation will be supplied in tables giving number and percentage by treatment group.

If applicable, patients treated but not considered as randomized, and patients randomized but not treated will be identified and described in separate listings.

Listings of patients with permanent treatment discontinuation, patients with premature end of study will be provided.

Additionally, a summary of all the analysis sets for safety and efficacy (Efficacy [ITT, m-ITT, OLE, and PSG], Safety, analysis set without trial impact (disruption) due to COVID-19 and analysis set with trial impact (disruption) due to COVID 19) will be summarized for the ITT analysis set by treatment group and overall using number and percentage.

A listing of patients excluded from analysis sets will be provided. Patients with permanent treatment discontinuation, patients with premature end of study will be identified and described in separate listings.

The reasons for being in the analysis set with trial impact (disruption) due to COVID-19 will be summarized for the modified ITT analysis set by treatment group and overall using number and percentage.

A listing of patients excluded from the analysis set without trial impact (disruption) due to COVID-19 will be provided.

The disposition of screened patients, screen failure patients, randomized and not treated patients, randomized patients, randomized and treated patients by country and site will be summarized for the screened analysis set by treatment group and overall using number and percentage.

A summary table to show patient disposition by visit according to trial impact (disruption) due to COVID-19 (visit not done, visit partially done on site, visit partially done by phone and visit done but delayed) will be provided. A summary table to show the patient disposition by visit according to trial impact (disruption) due to COVID-19 by country and site will be provided too.

5.2. Protocol Deviations

All critical or major protocol deviations including randomization and drug-dispensing irregularities will be summarized according to COVID-19 impact (i.e. deviations related to COVID-19 pandemic and deviations not related to COVID-19 pandemic) for the ITT analysis set by treatment group and overall using number and percentage.

A listing of patients with at least one critical or major protocol deviations will be provided.

Randomization and drug-dispensing irregularities occur whenever:

1. A randomization is not in accordance with the protocol-defined randomization method, such as a) an ineligible patient is randomized, b) a patient is randomized based on an incorrect stratum, c) a patient is randomized twice, or d) in a dynamic randomization scheme the treatment assignment is, in fact, not random, due to a computer program error.

OR

2. A patient is dispensed an IMP kit not allocated by the protocol-defined randomization, such as a) a patient at any time in the study is dispensed a different treatment kit than as randomized (which may or may not contain the correct-as-randomized IMP), or b) a non-randomized patient is treated with IMP reserved for randomized patients.

Randomization and drug-dispensing irregularities will be monitored throughout the study and reviewed on an ongoing basis.

All randomization and drug-dispensing irregularities will be documented in the clinical study report. If the number of irregularities is large enough to make a tabular summary useful, the critical or major irregularities will be categorized and summarized for the ITT analysis set by treatment group and overall using number and percentage. Non-randomized, treated patients will be described separately.

A listing of patients with at least one critical or major protocol deviations related to randomization and drug-dispensing irregularities will be provided.

Randomization and drug-dispensing irregularities to be prospectively identified include but are not limited to:

Table 5.2.1 Randomization and drug dispensing irregularities

Randomization and drug allocation irregularities

• Kit dispensation without IRT transaction• Erroneous kit dispensation• Kit not available• Randomization by error• Patient randomized twice• Stratification error

-
- Open-label kit dispensed instead of double-blind kit at Week 12
-

List of randomization and drug-dispensing irregularities will be provided by SANOFI.

6. Demographics and Baseline Characteristics

The demographics, patient characteristics and baseline disease characteristics will be summarized using the ITT and PSG analysis sets by treatment group and overall using descriptive statistics or using number and percentage. P-values on the treatment difference for the demographic and baseline characteristics data will not be calculated. In general, no specific description of the safety parameters will be provided at baseline. If relevant, the baseline values will be described along with each safety/efficacy analysis.

6.1. Demographics

The following demographics and patient characteristics will be summarized by treatment group and overall:

- Age (years),
- Age categories (≥ 18 to < 40 , ≥ 40 to < 65 , ≥ 65),
- Gender (Male, Female)
- Ethnicity (Hispanic or Latino, Not Hispanic or Latino, Not Reported, Unknown),
- Race (American Indian or Alaska Native, Asian, Black or African American, Native Hawaiian or Other Pacific Islander, Multiple, White, Not Reported, Unknown),
- Baseline body weight (kg) with grouping (< 70 , ≥ 70 to < 100 , ≥ 100),
- Baseline height (cm),
- Baseline body mass index (BMI) (kg/m^2) derived as: $(\text{Weight in kg})/(\text{Height in meters})^2$,
- Baseline BMI categories (< 15 , ≥ 15 to < 25 , ≥ 25 to < 30 , ≥ 30)
- Region (US [PSG, non-PSG], Europe and ROW)
- Alcohol habits at screening (Never, Occasional, At Least Daily, At Least Weekly, At Least Monthly)

6.2. Baseline Disease Characteristics

The following baseline disease characteristics will be summarized by treatment group and overall:

6.2.1. Sleep characteristics and sleep related impairment at baseline

- Rescaled Sleep quality NRS*
- SCORAD subjective sleep loss score (sleep VAS)
- PROMIS sleep disturbance short form 8a raw and T-scores
- Actigraphy
 - Sleep onset latency (SOL)*
 - Wake after sleep onset (WASO)*
 - Total Sleep Time (TST)*
 - Sleep efficiency (SE)*
- Sleep diary
 - SOL*
 - TST*
 - WASO*
 - SE*
 - Number of awakenings*
 - How rested the participant felt when getting up (NRS) *

- ESS score, and the categories as defined by
 - Lower Normal Daytime Sleepiness (0-5)
 - Higher Normal Daytime Sleepiness (6-10)
 - Mild Excessive Daytime Sleepiness (11-12)
 - Moderate Excessive Daytime Sleepiness (13-15)
 - Severe Excessive Daytime Sleepiness (16-24)
- PVT (Outcome metrics from data transfer)
 - Total errors
 - Number of lapses
 - Mean reciprocal response time (mean 1/RT)
 - Mean fastest response time (Fastest 10% RT)
 - Mean slowest reciprocal response time (Slowest 10% RT)
- ANAM: running memory, mathematical processing, procedural reaction time
 - Mean response time
 - Percentage of correct response
 - Throughput
- Polysomnography in the PSG analysis set (defined in 4.3.5)
 - SOL
 - WASO
 - TST
 - SE
 - Longest sleep episode
 - Stages of sleep
 - Arousal index

* average value of the assessment reported during the week prior to baseline visit

6.2.2. AD and associated disease characteristics at baseline

- Investigator's Global Assessment (IGA) score
 - Clear (0)
 - Almost clear (1)
 - Mild disease (2)
 - Moderate disease (3)
 - Severe disease (4)
- Body Surface Area (BSA) Involvement of AD
- EASI total score
- SCORAD overall score
- Peak pruritus NRS*
- Skin pain NRS*
- Skin sensitivity to touch NRS*
- Skin burn NRS*
- POEM score and categories as defined by
 - Clear or almost clear (0-2)
 - Mild eczema (3-7)
 - Moderate eczema (8-16)
 - Severe eczema (17-24)
 - Very severe eczema (25-28)
- DLQI total score
- HADS-Anxiety score, HADS-Depression score

- ACQ-5 total score
- AR-VAS score

6.2.3. Health economic endpoints at baseline

- WPAI-AD: currently employed status (yes/no); number of hours missed due to AD (only if employed); number of hours missed due to other reasons (only if employed); number of hours actually worked (only if employed); NRS of atopic dermatitis affected productivity while working (only if employed) and NRS of atopic dermatitis affected ability to do regular daily activities, other than work at job
- Day missed from school or from work due to AD : patients who were employed or enrolled in school were asked to report the number of sick leave/missed school days due to AD from each assessment since the last study visit, separately for employment/school status by full time and part time

6.3. Alcohol, Tobacco and Caffeine Usage

The following alcohol, tobacco and Caffeine habits will be summarized by treatment group and overall:

- Alcohol consumption: amount (glass) per day and per visit
- Caffeine consumption: amount (cup) per day and per visit
- Tobacco consumption: amount (cigarette) per day and per visit

The tobacco and caffeine data are only collected for PSG patients.

6.4. Medical History

6.4.1. General Medical History

Medical (or surgical) history includes all the relevant medical (or surgical) history during the lifetime of the patient.

Medical and surgical history will be coded to “lower level term (LLT)”, “preferred term (PT)”, “high level term (HLT)”, “high level group term (HLGT)”, and associated primary “system organ class (SOC)” using the version of Medical Dictionary for Regulatory Activities (MedDRA) in effect at Sanofi at the time of each database lock.

The number and percentage of subjects with any medical history will be summarized by treatment group and overall and for each SOC. SOC will be sorted in descending order of frequency based on the total of all treatment groups.

6.4.2. Disease-Specific History

Not applicable.

6.5. Inclusion and Exclusion Criteria

Inclusion and exclusion criteria will be presented for the screened analysis set for each treatment group and overall using number and percentage.

6.6. Other Background Information

Not applicable.

7. Treatments and Medications

7.1. Prior and Concomitant Medications

The prior and concomitant medications will be presented for the ITT analysis set for each treatment group and overall using number and percentage. No statistical test for the between-group difference will be performed.

All medications will be coded using the World Health Organization-Drug Dictionary (WHO-DD) using the version in effect at Sanofi at the time of each database lock.

Medications will be summarized by treatment group according to the WHO-DD, considering the first digit of the anatomic category (ATC) class (anatomic category) and the first 3 digits of the ATC class (therapeutic category). All ATC codes corresponding to a medication will be summarized, and patients will be counted once in each ATC category (anatomic or therapeutic) linked to the medication. Therefore, patients may be counted several times for the same medication.

The summaries for prior, concomitant, and post-treatment medications will be sorted by decreasing frequency of ATC followed by all other therapeutic classes based on the incidence in the dupilumab treatment group. In case of equal frequency regarding ATCs, alphabetical order will be used.

For the purpose of inclusion in prior and/or concomitant medication tables, incomplete medication start and stop dates will be imputed as described in [section 15.4.3](#).

7.1.1. Prior Medications

Prior medications are those the patient began prior to first IMP intake. Prior medications can be discontinued before first treatment administration or can be ongoing during the treatment phase.

7.1.2. Concomitant Medications

Concomitant medications are any treatments received by the patient concomitantly to the IMP, starting from the 1st administration of IMP to the date of last administration + 14 days (boundary not included). A given medication can be classified both as a prior medication and as a concomitant medication.

7.1.3. Post-treatment medications

Post-treatment medications are those the patient took (continued or initiated) in the period running from the 14th day after the last administration of IMP up to the end of the study.

7.2. Study Treatments

The extent of IMP exposure and compliance will be assessed and summarized separately within the double-blind treatment period, the OLE period (for compliance only) and overall period (combined double-blind and OLE periods) by actual treatment group and overall using the safety analysis set and analysis set with trial impact (disruption) due to COVID-19.

7.2.1. Extent of Exposure

The extent of IMP exposure will be assessed by the duration of IMP exposure.

Duration of IMP exposure is defined as last IMP administration dose date – first IMP administration dose date + 14 days, regardless of unplanned intermittent discontinuations.

Duration of IMP exposure will be summarized descriptively as a quantitative variable (number, mean, SD, median, Q1, Q3, minimum and maximum). In addition, duration of IMP exposure will also be summarized categorically by numbers and percentages for each of the following categories and cumulatively according to these categories:

- >0 and ≤2 weeks
- >2 and ≤4 weeks
- >4 and ≤8 weeks
- >8 and ≤12 weeks
- >12 and ≤16 weeks
- >16 and ≤20 weeks
- >20 and ≤24 weeks
- >24 weeks

Additionally, the cumulative duration of IMP exposure will be provided, defined as the sum of duration of IMP exposure for all patients, and will be expressed in patient years.

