6.3 MEASURES TO MINIMIZE BIAS: RANDOMIZATION AND BLINDING

A randomized treatment kit number list will be generated centrally by Sanofi for the IMPs. The IMPs (dupilumab or matching placebo) will be packaged in accordance with the list. The Sanofi Clinical Supply Chain team will provide the randomized treatment kit number list and the Study Biostatistician will provide the randomization scheme to the centralized treatment allocation system (Interactive Voice Response System/Interactive Web Response System [IVRS/IWRS]). This centralized treatment allocation system will generate the patient randomization list according to which it will allocate the IMP to the patients. The Investigator obtains treatment kit number at randomization and subsequent scheduled visits via an IVRS/IWRS that will be available 24 hours a day.

At some site visits, the interactive response technology (IRT) will allocate enough kits for site administration on same day and home administration that will be performed 2 weeks later.

Randomization will be stratified: PSG (regardless of geographic location), US (non-PSG), Europe (non-PSG) and ROW (non-PSG).

A participant who has been allocated to a randomized intervention regardless whether the intervention kit was used or not (ie, participant registered by the IRT) will be considered a randomized subject. A participant cannot be randomized more than once in the study.

Dupilumab and placebo will be provided in identically matched 2 mL pre-filled syringes. To protect the blind, each treatment kit of 2 mL (dupilumab / placebo) glass pre-filled syringes will be prepared such that the treatments (dupilumab and its matching placebo) are identical and indistinguishable and will be labeled with a treatment kit number

Patients will receive either;

- Dupilumab 600 mg (2 x 300 mg dupilumab injections) on Day 1 (ie, the loading dose), followed by 1 dupilumab injection of 300 mg Q2W until week 10, then 1 dupilumab +1 placebo injection at week 12 (to protect the blind while placebo patients receive their loading dose), followed by 1 dupilumab injection Q2W with last injection at week 22 or,
- Matching placebo for dupilumab (2 x 2 mL placebo injections) on Day 1 (ie, the loading dose), then 1 placebo injection Q2W until week 10, and then 2 x 300 mg dupilumab injections at week 12 (ie, the loading dose), followed by dupilumab injections Q2W with last injection at week 22.

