3.1. Overall Study Design and Plan

This is a Phase IV, prospective, 2:1 randomized, multinational, multicenter study, with a 12-week double-blind placebo-controlled period, followed by a 12-week open label extension to evaluate the effect of dupilumab on sleep in adult patients with moderate to severe AD.

[figure not shown]
Approximately 201 participants will be randomly assigned to study intervention in a 2:1 dupilumab to placebo ratio from multiple sites globally such that at least 150 evaluable participants (100 in the active group and 50 in placebo) complete the double-blind portion (to week 12) of the study.

The study will comprise of:

- Screening Period 1 (Day -28 to -8): Patients will be evaluated according to inclusion and exclusion criteria
- Screening Period 2 (Day -7 to -1; pre-baseline assessments): eligible patients will complete the daily sleep quality, daily pruritus, skin pain, skin sensitivity, and touch skin burn, sleep diary, and will wear an actigraph at night-time during the 7 days immediately preceding the Baseline visit (Day 1). If preferred by the patient and the investigator for logistical reasons, screening can be done during a single on-site visit. In that case, all procedures planned at screening 1 and screening 2 should be done during this single screening visit. Importantly, this single screening visit will have to be done at least 7 days before the baseline visit, as patients should wear the actigraph and complete the diary for 7 days before baseline.
- Baseline (Day 1): Patients who remain eligible will be randomized
- 12-week double-blind placebo-controlled period: Patients will be randomized to receive dupilumab or placebo
- 12-week open-label extension period: following completion of double-blind period, patients randomized to dupilumab will continue to receive active treatment for open-label period, whereas patients randomized to placebo will receive active treatment with dupilumab.

The maximum study duration per participant will be 28 weeks. A patient is considered to have complete the study if he/she has completed all phases of the study including the last scheduled visit shown in the Schedules of Activities (see [Appendix 15.2](#)).

Figure 3-1 Study Plan

Abbreviations: q2w=every 2 weeks

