4.1. Sample Size

The sample size calculations were based on the subset of patients who reported ≥ 5 units of baseline sleep loss and ≥ 3 units of baseline pruritus scores on the SCORAD instrument in a previous study (AD1424) evaluating efficacy of dupilumab for AD.

Since no previous data are available on daily sleep on the NRS scale, the SCORAD sleep component (VAS) data was used as a basis for the sample size determination for the primary endpoint. The variability (standard deviation) estimate for the subset of patients mentioned above was 37% for the % change from baseline to week 12. Given the uncertainty in the variability from this variable to the NRS weekly average sleep score, the above variability was inflated by $\sim 20\%$, and assumed to be 44% for the primary sleep parameter. With these assumptions, a total sample of 150 (50 in placebo and 100 in dupilumab group) patients will provide 90% power ($\alpha = 0.05$, 2-sided) to detect a treatment difference of 25% (effect size, $\Delta/\sigma = 0.57$) for the percent change from baseline.

For secondary actigraphy endpoints, sample size estimates are provided in reference to Nemolizumab Ph2 data at week 4. For TST, to detect a 30 minutes difference between treatments: (2:1 allocation ratio; $\alpha=0.05$, 2-sided), assuming the same variability at week 16 weeks as seen for Nemolizumab at week 4 (=56 min), then 167 subjects are needed to provide 90% power. Furthermore, the proposed sample size would have $>90\%$ power to detect a difference of 10% for change from baseline in actigraphy based sleep efficiency, assuming a variability of 11% ($\alpha=0.05$, 2-sided). The variability estimate was based on for actigraphy based sleep efficiency at week 4, inflated by 50% to account for possible increase in variability over time (from week 4 to week 16). Of note, the data used for actigraphy parameters are limited.

Allowing for 20% dropouts, a total of approximately 201 patients will be enrolled in the study.

Considering the uncertainty of the variability of the primary endpoint, when data are available for this endpoint from about 50% of the patients completing Week 12, the variability will be assessed in a blinded manner, and the sample size will be re-estimated. If the re-estimated sample size is higher than the original estimate, the sample size may be increased accordingly, not to exceed a total of 150 additional patients.

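### Read literally, the SAP's exposure rules count the placebo weeks of switched patients as dupilumab exposure, so the overall dupilumab row is about 20% too high

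*SAP*

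**What the plan says.** - **Formula.** SAP 7.2.1 takes the last IMP date minus the "first IMP administration dose date + 14 days, regardless of unplanned intermittent discontinuations". Cumulative exposure is "defined as the sum of duration of IMP exposure for all patients, and will be expressed in patient years". Durations are also summarised by mean, median and category.
- **Meaning of IMP.** Protocol 6.3: "The IMPs (dupilumab or matching placebo) will be packaged in accordance with the list".
- **Planned switch.** Placebo-arm patients receive two placebo injections on Day 1, "then 1 placebo injection Q2W until week 10, and then 2 x 300 mg dupilumab injections at week 12" (Protocol 6.3). Both arms have their last injection at week 22.
- **Periods.** SAP 7.2 covers the double-blind period, "the OLE period (for compliance only) and overall period (combined double-blind and OLE periods"), tabulated by actual treatment group and overall. Extension weeks therefore enter the exposure tables only through the overall period.
- **Group label.** SAP 4.3.6 (Safety Analysis Set) assigns patients who received both placebo and dupilumab to the dupilumab group for as-treated analysis. It makes no exception for the planned switch. The treatment labels in SAP Table 4.4.1 include none for placebo followed by dupilumab.
- **Size.** SAP 3.1: "Approximately 201 participants will be randomly assigned to study intervention in a 2:1 dupilumab to placebo ratio", so that "at least 150 evaluable participants (100 in the active group and 50 in placebo) complete the double-blind portion". SAP 4.1: "Allowing for 20% dropouts, a total of approximately 201 patients will be enrolled in the study".

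**The concern.** Every placebo-arm patient who enters the extension receives both products by design. The exposure clock starts at the first IMP dose, which for these patients is placebo, and nothing restarts it at the first dupilumab dose. Their whole duration then goes into the dupilumab row under 4.3.6. That row will be read as time on dupilumab, but part of it is time on placebo.

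Adverse events through Week 24 are a secondary endpoint, and safety is reported for the overall period by actual treatment group. A reader uses the exposure table to judge how much drug time lies behind those counts. The distribution is affected as well as the total: switched patients appear as long-exposure dupilumab patients when they had half that time on the drug. No planned table directly reports dupilumab exposure in switched patients.

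**Working it through.** The documents state no exposure figure, so there is none to reproduce. The calculation applies the SAP 7.2.1 formula to the dosing schedule.

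**Inputs.** 201 patients at 2:1 give 134 dupilumab and 67 placebo (SAP 3.1). Day 1 is the first dose, the week 10 dose falls on Day 71 and the week 22 dose on Day 155. Patient-years = days / 365.25.

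**Duration per patient, dosed on schedule.**
- Double-blind: 71 − 1 + 14 = 84 days = 12 weeks.
- Overall: 155 − 1 + 14 = 168 days = 24 weeks.
- Dupilumab in a switched patient: 168 − 84 = 84 days = 12 weeks.

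**Exposure actually received, full completion.**
- Dupilumab: (134 × 168 + 67 × 84) / 365.25 = 28,140 / 365.25 = 77.0 patient-years.
- Placebo: 67 × 84 / 365.25 = 15.4.
- All IMP: 201 × 168 / 365.25 = 92.5.

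**What the tables would show.**

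| Table and labelling | Row | Shown | Received | Difference |
|---|---|---|---|---|
| Overall, 4.3.6 as written | Dupilumab | 201 × 168 / 365.25 = 92.5 | 77.0 | +20% |
| Double-blind, 4.3.6 also applied | Dupilumab | 201 × 84 / 365.25 = 46.2 | 134 × 84 / 365.25 = 30.8 | +50% |
| Overall, randomised arm | Dupilumab | 134 × 168 / 365.25 = 61.6 | 61.6 in that arm; 77.0 in both arms | 0% for the arm; −20% against all dupilumab |
| Overall, randomised arm | Placebo | 67 × 168 / 365.25 = 30.8 | 15.4 | +100% |

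**Distribution under 4.3.6.** Mean exposure in the dupilumab row reads 168 days (24 weeks). Mean dupilumab exposure in those 201 patients is 28,140 / 201 = 140 days (20 weeks). All 67 switched completers, one third of the row, fall in the category for over 20 and up to 24 weeks. Their dupilumab exposure belongs in the category for over 8 and up to 12 weeks.

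**Dropout.** Dropouts are assumed to contribute 6 weeks in the period in which they leave. Figures are patient-weeks in the overall dupilumab row under 4.3.6. Placebo patients who never switch stay in the placebo row.
- 150 double-blind completers (34 and 17 drop out): received 100 × 24 + 34 × 6 + 50 × 12 = 3,204; shown 3,204 + 50 × 12 = 3,804; +18.7%.
- 20% in each arm (27 and 13): received 107 × 24 + 27 × 6 + 54 × 12 = 3,378; shown 3,378 + 54 × 12 = 4,026; +19.2%.
- 10% dupilumab, 30% placebo (13 and 20): received 121 × 24 + 13 × 6 + 47 × 12 = 3,546; shown 3,546 + 47 × 12 = 4,110; +15.9%.
- Dropout in the extension only, 20% (27 and 13): received 107 × 24 + 27 × 18 + 54 × 12 + 13 × 6 = 3,780; shown 3,780 + 67 × 12 = 4,584; +21.3%.

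**The case against.** The strongest reply is that the SAP defines duration of IMP exposure, and IMP includes placebo, so the figure is accurate for what it is called. That stands for the all-patient total: 92.5 patient-years is correct as IMP exposure. It does not cover a row labelled dupilumab that holds placebo weeks.

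The 4.3.6 rule may have been meant for dispensing errors, in which case a programmer might tabulate by randomised arm. The dupilumab row would then be right for patients randomised to dupilumab, and total dupilumab exposure could be recovered by subtraction (92.5 − 15.4 = 77.0). But 15.4 dupilumab patient-years would sit under placebo, that row would be double its true placebo exposure, and the distribution in switched patients would still not be shown. Table layouts are in a separate shell document and may split these patients. The SAP text does not require it.

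Three stronger readings are tempting, and the documents do not support them:
- A reader might infer that the error carries into the adverse event incidences. SAP 9.1 divides by the number of patients in the safety analysis set, and no exposure-adjusted rate is planned.
- A reader might infer that the extension is left out of exposure. Its weeks are in the overall period; only a separate extension table is missing.
- A reader might infer that dupilumab exposure is about 20% wrong under any label. The 20% excess is the literal plan. The 20% shortfall arises only under the alternative reading, and only against dupilumab exposure in both arms.

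**Conclusion.** The point holds as a labelling and definition error in the exposure tables. Sections 7.2, 7.2.1 and 4.3.6, read together and literally, give an overall dupilumab row of 92.5 patient-years against 77.0 received. The 20% assumes that all 201 patients complete on schedule. It does not depend on the total sample size at 2:1 allocation. The scenarios with double-blind dropout give about 16% to 19%, and dropout confined to the extension gives about 21%. The 50% excess in the double-blind table arises only if 4.3.6 is applied there too, which its wording permits.

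No efficacy result or hypothesis test is touched, and patient-years enter no adverse event percentage. The correction should still be made, because a stated rule produces a wrong headline exposure figure and is cheap to amend.

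**What to change.** 1. **SAP 4.3.6.** State that the rule for patients who received both products does not relabel those who switch as planned at Week 12, so that double-blind tables use the treatment received in that period.
2. **SAP 7.2 and 7.2.1.** Compute exposure by product.
   - Placebo, for patients treated with placebo in the double-blind period: first dose to last double-blind dose + 14 days, cut at the first open-label dose.
   - Dupilumab: first dupilumab dose (Day 1 or Week 12) to last dupilumab dose + 14 days.
   - The masking placebo syringe given to the dupilumab arm at Week 12 does not count as placebo exposure.
3. **Tables.** Add extension-period exposure by randomised arm, and report total dupilumab patient-years over both arms.

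The cost is SAP wording and one more table from dose dates already collected. The stated dupilumab patient-years become smaller. Trial conduct and the efficacy analyses do not change.
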